Official Title: Effects of a Mobile Application RA Joint Protection and Activity Self-management Program

NCT number: NCT05570175

Date of the document: 20180801

Background

Physical activity and joint care are the import parts for the rheumatoid arthritis (RA) patients because physical disability is the most common outcome of RA (Chiou et al., 2009; Flurey et al., 2014). The synovial joints inflammation causes pain and stiffness, and turning simple daily activities into challenges (Chiou et al., 2009; Swann, 2011; HO, 2014). The symptoms of RA can vary considerably from day-to-day and alter throughout each day which is especially prominent in the morning or after prolonged sitting (Swann, 2011). When the disease is not in an active stage, the swelling reduces but the joint capsule remains stretched and unable to maintain its correct position, and can affect other parts of the body (Swann, 2011). Unfortunately, RA patients tend to lack of physically activity because they believed it is unsafe to exercise their joints, or had concerns that increased activity would exacerbate their pain (Breedland et al., 2011; Chang et al., 2014).

Diagnosis of RA most often occurs at 40 years of age and older (Lin et al. 2004), as life span is increasing in Taiwan (Ministry of the Interior, Department of Statistics, 2016), RA patients living with the disease for more than 40 years. These conditions cannot be cured, but can be managed through education, and self-management (Davies, 2010). The evidences from literature presented that there are some limitations in traditional self-management interventions (Azevedo et al., 2015; Lorig et al., 2010; Shigaki, et al., 2013; Stinson et al., 2014). The most important issue is it is difficulty in involving all patients (Azevedo et al., 2015). Many patients find it difficult to participate in office-based programs because they are out of town or due to pain or functional limitations (Shigaki, et al., 2013). One solution to mitigate some of these problems is exploiting the benefits of modern technologies such as cellular phones (Allam et al., 2015; Azevedo et al., 2015).

The health care domain, like many other fields, benefits from this technological advancement; people tend to seek online health information, virtual communities, and Web-based apps, and many other forms of online health services have started to emerge to satisfy people's needs (Allam et al., 2015).

Methods

Research Design

An *experimental design* was used to examine the effects of a mobile application RA joint protection and activity self-management program

Sample and Setting

A medical center in northern Taiwan was selected as the research setting to ensure sufficient numbers of RA patients are able to be recruited for this study, and the teaching hospital is constantly striving to improve their services, and is readily accessible to the researcher. Patients who visited the rheumatology departments of the medical center was eligible for the study and the **inclusion criteria include**: diagnosis of RA, age of 20 years or over, disease considered by the treating rheumatologist to have been stable for at least 12 weeks, able to communicate with researcher, and use a smartphone. Patients were excluded if they are suffering from other terminal illnesses, severe dementia or another debilitating psychiatric disorder, or living in a long-term care facility. **All patients were under the medical care of their rheumatologist during the study.**

Sampling Procedure

Patients with rheumatoid arthritis were approached for recruitment by research assistants when they were admitted to the clinic at the rheumatology departments of the medical centers. If the patients met the inclusion criteria, agreed to participate in the study, and signed informed consent was obtained, baseline data were collected. Following collection of baseline data, an independent researcher randomly assigned participants to the intervention or control group using a computerized allocation procedure in SPSS 22.0 for Windows; sequential numbers were generated and placed in sealed opaque envelopes, which designated the two groups. Thus, neither the participants nor the

researcher was aware of the group assignment until after the baseline questionnaire had been completed. The CONSORT (Consolidated Standards of Reporting Trials) flow diagram (Moher et al., 2001) was followed to manage the random allocation.

Intervention Program

The smartphone app was designed to facilitate a self-management program for patients with rheumatoid arthritis (Shao et al., 2021), which focused on joint activity and protection because these are recognized as vital aspects of managing symptoms of arthritis (Chaleshgar-Kordasiabi et al., 2018). The design of the program was guided by the literature regarding self-management for patients with rheumatoid arthritis (Domin et al., 2022) as well as the opinions and expectations of patients and healthcare experts about what should be included in a web-based rheumatoid arthritis self-management program. Feedback from patients and healthcare experts was integrated into our smartphone app to fit the needs of patients with rheumatoid arthritis.

Instruments and Outcome Measurements

Many of the standard measuring instruments selected have been used in previous studies of people with arthritis, and have established reliability and validity. Outcome data were collected at the baseline, and 2, and 3 months including RA disease activity (DAS-28), arthritis self-efficacy (ASE), physical functioning (MHAQ), and self-management behaviors.

Procedure and Data Collection

We evaluated whether the app facilitated changes in self-management strategies and improved outcomes by examining differences in data collected at baseline (T0) with data collected at 8-weeks (T1) and 12-weeks (T2) after commencement of the program for the intervention group compared with the control group. Self-report questionnaires were used to measure variables considered important for assessing the effectiveness of a self-management intervention: disease activity (symptoms of rheumatoid arthritis), arthritis self-efficacy, physical functioning, and self-management behaviors (Barlow et al., 2002). These self-report questionnaires, described below, have been shown to be reliable and valid instruments for patients with arthritis.

Data Analysis

Data were analyzed using the statistical software package SPSS 22 (IBM SPSS, Armonk, NY: IBM Corp), and .05 significant level was set. We tested the intervention effect by using GEE models. A robust standard error was calculated for consistent parameter estimates and an exchangeable working correlation matrix was used to account for the outcome dependency within individual participants (Liang & Zeger, 1986). Each GEE model included main effects of group (intervention *vs.* control), time (month *vs.* baseline) and two-way interaction effects (group x time). The group difference in the change from baseline to 2-months, or 3-months between two groups was verified when the two-way interaction effect(s) (group x time) was statistically significant.

Ethical Considerations

This study was reviewed and approved by the Institutional Review Boards of the hospitals of the primary investigator prior to data collection (No. 201702125B0, Date of Approval: 2018/01/08). The program occurred on a secure online platform and participant confidentiality was protected throughout all phases of the study in accordance with the University ethics guidelines. Only the research team had access to study data and only de-identified data were transmitted to coinvestigators. All patients were assured their anonymity and confidentiality would be preserved, and they could withdraw from the study at any time and for any reason. Signed informed consent was obtained from all participants prior to beginning the study.

References

Abshire, D. A., McDonnell, K. K., Donevant, S. B., Corbett, C. F., Tavakoli, A. S., Felder, T. M., & Pinto, B. M. (2021). Pivoting nursing research and scholarship during the COVID-19 pandemic. *Nursing Research*, 70(3), 165–172.

<https://doi.org/10.1097/NNR.0000000000000493>

Bandura, A. (1977). *Social learning theory*. Englewood Cliffs, NJ: Prentice Hall.

**Official Title: Effects of a Mobile Application RA Joint Protection and Activity**

**Self-management Program**

**NCT number: NCT05570175**

**Date of the document: 20180801**

**Statistical analysis plan**

Data were analyzed using the statistical software package SPSS 22 (IBM SPSS, Armonk, NY: IBM Corp), and .05 significant level was set. We tested the intervention effect by using GEE models. A robust standard error was calculated for consistent parameter estimates and an exchangeable working correlation matrix was used to account for the outcome dependency within individual participants (Liang & Zeger, 1986). Each GEE model included main effects of group (intervention *vs.* control), time (month *vs.* baseline) and two-way interaction effects (group x time). The group difference in the change from baseline to 2-months, or 3-months between two groups was verified when the two-way interaction effect(s) (group x time) was statistically significant.

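### Read as an ordinary sandwich variance with normal or chi-square critical values, the group-by-time test exceeds its .05 level, noticeably at about 30 per arm or fewer and by half a point or less from about 100 per arm

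*SAP*

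**What the plan says.** The SAP (Statistical analysis plan) and the Protocol (Data Analysis) carry the same text. The software is given by "Data were analyzed using the statistical software package SPSS 22", and the level (.05) by "05 significant level was set". The method is stated as "We tested the intervention effect by using GEE models". On the variance and correlation the SAP says "A robust standard error was calculated for consistent parameter estimates and an exchangeable working correlation matrix was used". Each model has group, time and their interaction. A difference in change at 2 or 3 months is "was verified when the two-way interaction effect(s) (group x time) was statistically significant".

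The Protocol (Instruments and Outcome Measurements) gives three time points and four outcomes: DAS-28, arthritis self-efficacy, MHAQ and self-management behaviors. The rule therefore applies to four models, each with two interaction terms.

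Neither document names a test statistic, a reference distribution, a small-sample correction, a sample size, an allocation ratio or a dropout rate. Neither says whether the two interaction terms are tested one at a time or together.

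**The concern.** The sandwich variance is justified for a large number of patients. In a finite sample two things push the test the same way. The plain sandwich is biased downwards, because residuals are taken from fitted means and no allowance is made for having fitted them. Normal or chi-square critical values also treat that variance as known when it is estimated. Both make a false positive more likely than the stated level.

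A claim for each outcome rests on crossing .05, so the level should be roughly what the plan says it is. Nothing in the documents ensures this. No correction is specified, and no stated sample size is large enough to make one unnecessary.

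**Working it through.** There is no figure in the plan to reproduce, since .05 is a chosen level. The check is what error rate the described test would have.

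**Inputs from the documents.** Level .05; robust standard error; exchangeable working correlation; group, time and group-by-time terms; three time points.

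**Assumptions.** Two-sided test; ordinary sandwich variance; normal or chi-square critical values (1.960 and 5.991); n patients per arm with N = 2n; complete normal data; the same covariance in both arms. N is unknown, so n runs from 15 to 100.

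**Step 1: what the sandwich is here.** With complete data and this saturated mean model, the interaction estimates are differences between arms in mean change from baseline. The sandwich variance is then the within-arm covariance of the changes with divisor n instead of n-1. A GEE fit to simulated data agreed with this to all printed digits.

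**Step 2: exact error rates.** Write ν = 2n-2.

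- Single contrast: 2·P(t with ν df > 1.960·√((n-1)/n)).
- Joint test of both terms: P(F with 2 and ν-1 df > 5.991·((n-1)/n)·(ν-1)/(2ν)).

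At n = 30, ν = 58. The single threshold is 1.960 × √(29/30) = 1.927, giving 5.9%. The joint threshold is 5.991 × (29/30) × 57/116 = 2.846, giving 6.6%.

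| Per arm (N) | ν | Single threshold | Single error | Joint threshold | Joint error |
|---|---|---|---|---|---|
| 15 (30) | 28 | 1.893 | 6.9% | 2.696 | 8.6% |
| 30 (60) | 58 | 1.927 | 5.9% | 2.846 | 6.6% |
| 50 (100) | 98 | 1.940 | 5.5% | 2.906 | 6.0% |
| 100 (200) | 198 | 1.950 | 5.3% | 2.951 | 5.5% |

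Simulation with 100,000 trials per setting agreed. Raising the within-patient correlation from .5 to .8 made no material difference. With arms of 20 and 40 and equal variances, the simulated errors were about 6.3% (single) and 7.5% (joint).

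**Step 3: the same test after correction.** With divisor n-1 and t critical values on N-2 df, the single contrast has error 5.0% at every n. For the joint test with F critical values on 2 and N-2 df, the error is P(F with 2 and ν-1 df > F(.95; 2, ν)·(ν-1)/ν). At n = 30 the threshold is 3.156 × 57/58 = 3.101. The errors are 5.6%, 5.3%, 5.2% and 5.1% at 15, 30, 50 and 100 per arm.

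Both parts are needed. With divisor n-1 but normal or chi-square critical values, the errors at 30 per arm are still 5.5% (single) and 6.1% (joint).

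**Step 4: cost in width.** For a single contrast the ratio of corrected to uncorrected width is √(n/(n-1)) × t(.975; 2n-2)/1.960. At 15 per arm this is 1.035 × 2.048/1.960 = 1.08. At 30, 50 and 100 it is 1.04, 1.02 and 1.01.

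**Step 5: unequal arms and variances.** Arms of 20 and 40, with half the SD in the larger arm, were simulated as a stress case. The ranges cover repeated runs.

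| Method | Single error | Joint error |
|---|---|---|
| Plain sandwich, normal/chi-square | 6.5-7.0% | 8.5-8.7% |
| Corrected sandwich, t/F on N-2 df | 5.4-5.6% | 6.7-6.8% |
| Mixed model with one covariance pooled over arms | 10.8-11.3% | 14.3-14.5% |

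**The case against.** The strongest reply is that the plan uses the standard robust variance from the GEE paper it cites, and that any harm depends on a sample size nobody can read from the documents. The Protocol (Sample and Setting) says the site was chosen so that enough patients could be recruited, and nothing there supports 15 per arm. At 50 per arm the single-contrast excess is half a point. This stands as a limit on the size of the point. It does not remove it, because the plan gives neither a sample size nor a correction.

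Three stronger readings are tempting, and the documents support none of them.

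- **That the plan specifies an uncorrected Wald chi-square test.** It names neither the statistic nor the reference distribution. The ordinary form is inferred from silence, though it is the natural reading of the text.
- **That the larger joint-test figures are the plan's error rates.** The phrase "verified when the two-way interaction effect(s) (group x time) was statistically significant" can mean one 2-df test or two separate contrasts. If either contrast alone may carry the claim, the chance of a false positive per outcome is about 9.5-12.5% for N of 200 down to 30. Most of that comes from having two chances, which is a separate matter of the decision rule.
- **That the planned confidence intervals are too narrow.** No interval is mentioned in either document. The width ratios apply only if intervals are reported.

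**Conclusion.** The point holds in a limited form. Under the natural reading, the test exceeds .05 at every sample size examined, and the joint test exceeds it by more than a single contrast does. At 30 per arm the excess is about 0.9 points for a single contrast and 1.6 points for the joint test. By 100 per arm it is about 0.3 and 0.5 points. It therefore matters mainly at about 30 per arm or fewer, and is close to negligible from about 100 per arm.

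A reader might infer that the .05 level fails seriously whatever the trial's size. The documents do not support that, because N is not stated and the excess shrinks steadily as N grows.

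The exact figures rest on equal arms, complete normal data and equal covariances. Unequal arms made the excess somewhat larger in the cases tried. Dropout was not modelled. This is a worthwhile refinement to the plan and does not by itself undermine it.

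**What to change.** Keep the GEE, the mean model and the tested terms. In the SAP, and in the matching Protocol section:

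1. State the number of patients analysed per arm, and whether group-by-time is tested jointly or per contrast.
2. Specify a bias-corrected sandwich variance. With complete data this means divisor n-1 within each arm; with missing visits, the general bias-corrected form is needed.
3. Specify t critical values (single contrast) or F critical values (joint test) on N-2 degrees of freedom. The variance correction alone is not enough, above all for the joint test.

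Do not treat a mixed model with one covariance pooled over arms as interchangeable with this. It gives up the sandwich's protection when arm sizes and variances differ. In the stress case above it did worse than the uncorrected test, while the corrected sandwich did better than both.

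The cost is a few lines of SAP text and a little extra analysis work. The documents do not show whether the named software offers the correction directly, so this should be checked. With equal arms and complete data it amounts to multiplying the sandwich variance by n/(n-1). Critical values, and any intervals reported, become about 1% wider at 100 per arm and 8% wider at 15 per arm, with a correspondingly small loss of power.

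### A precision gain left unused, not an error: the planned GEE tests an unadjusted difference in change and does not use the pre-randomisation baseline as a covariate

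*SAP*

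**What the plan says.** The SAP's single section and the protocol's Data Analysis section carry the same text. "Each GEE model included main effects of group", then time, then the two-way interaction; no other term is named. On the dependence between visits, "an exchangeable working correlation matrix was used to account for the outcome dependency within individual participants", with robust standard errors. The decision rule rests on the interaction: "The group difference in the change from baseline to 2-months, or 3-months between two groups was verified" when that term is significant. Baseline therefore enters as a response record (T0), not as a covariate.

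The protocol's Sampling Procedure fixes the order of events: "Following collection of baseline data, an independent researcher randomly assigned participants to the intervention or control group". It adds that no participant and no "researcher was aware of the group assignment until after the baseline questionnaire had been completed". On the allocation itself, "sequential numbers were generated and placed in sealed opaque envelopes, which designated the two groups"; no ratio is given. The Instruments section lists the outcomes taken at baseline and at both follow-ups, "including RA disease activity (DAS-28), arthritis self-efficacy (ASE), physical functioning (MHAQ), and self-management behaviors", so each follow-up value has a baseline value of the same measure.

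**The concern.** A difference in change subtracts the baseline with weight 1. After randomisation, with equal arms or a common slope, the most precise weight is the slope of follow-up on baseline, which is usually not 1. When the slope is below 1, subtracting the whole baseline over-corrects for any chance imbalance between the arms and adds noise to the comparison. It is easy to suppose that the exchangeable correlation takes care of this. If it does not, the confidence intervals at T1 and T2 may be wider than the collected data require. Neither document states a sample size or power, so spare precision cannot be taken for granted.

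**Working it through.** **Inputs.** From the documents: the model terms, the exchangeable structure, the robust SE, baseline before allocation, and visits at T0, T1 (8 weeks) and T2 (12 weeks). Assumed, because the documents are silent: identity link; baseline-to-follow-up correlation ρ; SD ratio k = SD(follow-up)/SD(baseline); allocation; slopes by arm; sample size. The plan states no precision or power figure, so there is none to reproduce.

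**Step 1: what the planned interaction estimates.** The planned GEE was fitted to one simulated complete data set (50 per arm, ρ = 0.6). The interactions were 0.0710 at T1 and 0.0460 at T2, equal to the raw differences in mean change. The robust SEs (0.1548 and 0.1611) also equalled the SEs of those differences. With complete data, the working correlation does not change the weight given to baseline.

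**Step 2: variance of the two contrasts.** With 1:1 allocation, per patient and in units of the baseline variance:

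- planned: 1 + k² − 2ρk
- adjusted: k²(1 − ρ²)
- planned minus adjusted: (1 − ρk)², which is never negative and is zero when the slope ρk = 1

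At k = 1 the ratio adjusted/planned is (1 − ρ²)/[2(1 − ρ)] = (1 + ρ)/2. For ρ = 0.5 this is 0.75, a 25% cut.

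| ρ | k = 1: cut in variance (in SE) | k = 1.25: cut in variance | k = 0.8: cut in variance |
|---|---|---|---|
| 0.3 | 35% (19%) | 22% | 50% |
| 0.5 | 25% (13%) | 11% | 43% |
| 0.7 | 15% (8%) | 2% | 37% |
| 0.8 | 10% (5%) | 0% | 36% |
| 0.9 | 5% (3%) | 5% | 39% |

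The zero at ρ = 0.8, k = 1.25 is the case where the slope is 0.8 × 1.25 = 1.

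**Step 3: finite samples.** Simulation with no effect (T2, 60 per arm, 20,000 runs) gave adjusted/planned ratios of 0.653, 0.758, 0.864, 0.910 and 0.957 at k = 1, close to 0.65, 0.75, 0.85, 0.90 and 0.95. Where the slope is 1, the ratio was 1.009 at 60 per arm and 1.017 at 30 per arm: a cost of 1–2%. The type I error of the robust test at 30 per arm was 5.98–6.25% adjusted against 5.65–6.07% planned. At 60 per arm it was 5.3–5.8% against 5.1–5.7%.

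**Step 4: missing follow-up.** If a random 20% lose both follow-ups (fraction kept f = 0.8, k = 1), the ratio is (1 + ρ)/[1 + ρ + f(1 − ρ)].

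- ρ = 0.5: 1.5/1.9 = 0.789, a 21% cut instead of 25%
- ρ = 0.8: 1.8/1.96 = 0.918, an 8% cut instead of 10%

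The planned model then recovers a small part of the gain. Dropout that depends on outcome or arm was not examined.

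**Step 5: unequal arms with different slopes.** With baseline SD 1 and residual SD 0.6, a weight w on baseline gives V(w) = [(b₁ − w)² + 0.36]/n₁ + [(b₀ − w)² + 0.36]/n₀. Take n = 120 and 60, with slopes 0.5 and 1.1:

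- planned, w = 1: 0.61/120 + 0.37/60 = 0.01125
- pooled slope, w = (2/3)(0.5) + (1/3)(1.1) = 0.7: 0.40/120 + 0.52/60 = 0.01200, ratio 1.067
- with a group x centred-baseline term, w = (1/3)(0.5) + (2/3)(1.1) = 0.9: 0.52/120 + 0.40/60 = 0.01100, ratio 0.978

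Slopes of 0.6 and 1.2 give 1.091 and 1.000. A single pooled slope can therefore lose 7–9% in such a setting.

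**The case against.** The best case against acting is that nothing is wrong. Difference in change is a legitimate, pre-stated estimator. A reader might infer that the planned test is biased or invalid; the documents do not support that. Baseline precedes allocation, so both estimators are unbiased over repeated randomisation, and in simulation under no effect both centred on zero.

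The size of the gain is also assumed throughout. A reader might take the 25% or 35% figure as this trial's gain, but no ρ or SD is given for any of the four outcomes. The only clue is the entry criterion, "disease considered by the treating rheumatologist to have been stable for at least 12 weeks". It makes a high ρ plausible for DAS-28 alone, and with equal SDs that means the low end, 5–10% of variance at ρ of 0.8–0.9.

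The change is not free, and it has less value if the analysis is finished. The SAP's past tense, and citations from 2021 and 2022 in the protocol's Intervention Program section, suggest that it is. An adjusted result would then be post hoc and could not replace the planned one.

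All of this stands. It limits the point to an improvement of unknown size. It does not remove it, because the covariate is already in hand and the possible loss is small unless allocation is unequal and slopes differ by arm.

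**Conclusion.** The point holds as a cheap improvement in precision, worth making but not needed for validity. With complete data and an identity link, the planned contrast makes no baseline adjustment. With 1:1 allocation or a common slope, adjustment cannot increase the large-sample variance and reduces it unless the slope is 1. To give a sense of scale: had the planned contrast 80% power, adjustment with equal SDs would give about 93.5%, 90%, 86%, 84% and 82% at ρ of 0.3, 0.5, 0.7, 0.8 and 0.9. These figures illustrate assumptions and are not estimates for this trial. With incomplete follow-up the advantage is somewhat smaller, because the exchangeable structure already recovers part of it.

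**What to change.** For each outcome, take the T1 and T2 values as the responses in the GEE, with group, time, group x time, the T0 value of the same outcome, and T0 value x time. Report the adjusted group difference at T1 and at T2, each with a robust 95% confidence interval, and judge the effect on these. The decision rule must be reworded: once T0 is no longer a response, group x time tests only whether the effect differs between the two visits. With T1 as the reference visit and no group x baseline term, the T1 effect is the group coefficient and the T2 effect is that coefficient plus the interaction.

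Two shortcuts do not do the job:

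- Adding baseline as a covariate while T0 stays among the responses does not give this adjustment.
- Deleting the group main effect from the three-visit model does not force equal baseline means when group and time are factors. In one simulated data set (60 per arm, ρ = 0.5) the software refitted a group term at every visit, baseline included. The T1 and T2 terms became raw cross-sectional differences (0.0624 and −0.0959). The truly constrained model gave 0.1092 and −0.0491. It needs hand-built group x T1 and group x T2 indicators, and its precision depends on the SDs and on the T1–T2 correlation, so it is not a good default here.

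If allocation was unequal, add group x centred baseline at each visit and bootstrap the SE, because the robust SE treats the centring mean as fixed.

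The cost is revised SAP wording, a restructured data set and a new decision rule, with no new data or patients. Participants with no follow-up value leave the model. The statistical costs are those in steps 3 and 5 of the working. If the analysis has been run, keep the planned result and show the adjusted model beside it, labelled post hoc.
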